7.9 Pulmonary Embolism Severity Index and Simplified Pulmonary Embolism Severity Index

PESI/sPESI will be calculated at Screening/Baseline, within 4 hours Post-APT treatment , at 24 (\pm 6) hours and at 48 (\pm 6) hours after the start of the APT Procedure. Refer to Appendix B for PESI/sPESI scoring information.

7.10 Laboratory Tests and Biomarkers

The following laboratory tests will be performed at Screening/Baseline, within 4 hours of the end of the APT procedure and at 48 (\pm 6) hours after the start of the APT Procedure.

- Hemoglobin, Hematocrit
- Platelet count
- Bleeding Times:
 - aPTT (seconds to form a blood clot in a sample of blood through measurement of the amount and function of coagulation factors);
 - PT and INR – prothrombin time (PT; time for clot to form in a sample of blood). Internationalized Normalized Ration (INR; adjusts for changes in the PT reagents)
- Kidney Tests: BUN (blood urea nitrogen), Creatinine

In addition, the following biomarker laboratory tests will be performed at Screening/Baseline, and 48 (\pm 6) hours after the start of the APT Procedure:

- Cardiac troponin : used to detect and evaluate mild to severe heart injury, and to distinguish chest pain that may be due to other causes. Elevations may indicate some degree of damage to the heart.
- BNP/NT-proBNP: produced primarily by the left ventricle of the heart. It is associated with blood volume and pressure and with the work of the heart. When the left ventricle of the heart is stretched, BNP concentrations increase.
- D-Dimer: a fibrin degradation product that reflects endogenous fibrinolysis.
- Lactate/Lactic acid: used to determine if lactic acidosis is present. Lactic acid is a product of cell metabolism that can accumulate when cells lack sufficient oxygen (hypoxia) and must turn to a less efficient means of energy production, or when a condition causes excess production or impaired clearance of lactate. For laboratories that do not measure lactate, lactic acid may be substituted.

At select participating sites, additional biomarker laboratory tests will be performed to assess thrombolytic activity at Screening/Baseline, at the end of the APT procedure, and at 48 (\pm 6) hours after the start of the APT Procedure. They include:

- Tissue plasminogen activator (t-PA) antigen to give the level of plasma t-PA
- Plasmin-antiplasmin levels- a marker of plasmin activation/turnover. Plasmin is the most powerful enzyme in the body and no free plasmin is found as any not bound to surface receptors binds to its inhibitor alpha-2 antiplasmin. Thus the quantity of plasmin-antiplasmin reflects how much plasmin is being generated.
- D-dimer ELISA (highly sensitive) – a marker of fibrinolytic turnover. This will provide a marker of turnover/amount of fibrinolysis
- Plasminogen activator inhibitor -1 (PAI-1) – a regulator of t-PA that binds to t-PA to inhibit it.
- Thrombin generation – a marker of thrombin activation which will demonstrate the ability of the coagulation system to work effectively and produce thrombin?
- Prothrombin factor 1+2 –a marker of thrombin activation, cleaved off from prothrombin when thrombin is generated
- Soluble S100A10. A receptor on the endothelium for plasminogen.

7.11 Anticoagulation and Concomitant Medications

Concomitant (non-anticoagulation) medications will be recorded on the Concomitant eCRF from Screening/Baseline through the 12 month follow-up period for medications prescribed to treat a serious adverse event only.

Anticoagulation history will be obtained at Screening/Baseline for the **3 days prior** to start of the APT procedure. Patient is excluded if thrombolytics or glycoprotein IIb/IIIa antagonists given **within 3 days prior** to start of APT Procedure. Changes in anticoagulation medications will be recorded on the Anticoagulant eCRF throughout the 12-month follow-up period.

7.12 6 Minute Walk Test (6MW)

Exercise testing will be performed at all follow-up clinic visits and in the event of early termination. Subjects will be evaluated with a 6MW and BORG Dyspnea scale (Appendix D).

7.13 Quality of Life (QOL) Assessments: PEmb-QOL and EQ-5D-5L

Two QOL Instruments will be used in this study and are included in Appendix E. The PEmb-QOL and EQ-5D-5L will be administered at follow-up during Days 30 (± 5 d), 90 (± 10 d), 365 (± 14 d), and Early Termination.

8 SAFETY REPORTING

8.1 Adverse Events

An adverse event (AE) is defined as any untoward medical occurrence observed in a subject that develops or worsens from Screening/Baseline, whether or not considered intervention related. An AE can be any unfavorable and unintended sign, symptom, or disease temporally associated with the use of an intervention and does not imply any judgment about causality.

8.2 Serious Adverse Events (SAE)

An AE is considered “serious” if, in the view of either the investigator or sponsor, it results in any of the following outcomes:

1. Death
2. Life-threatening (had the event occurred in a more severe form, might have caused death)
3. Inpatient hospitalization or prolongation of existing hospitalization

4. Permanent impairment of a body structure or body function; a persistent or significant incapacity or substantial disruption of the ability to conduct normal life functions, for example, persistent or significant loss of function, disability, or incapacity
5. Congenital abnormality or birth defect if subject should become pregnant within 90 days of the treatment completion
6. Important medical events that may not result in death, be life-threatening, or require hospitalization may be considered serious when, based upon appropriate medical judgment, they may jeopardize the subject and may require medical or surgical intervention to prevent one of the outcomes listed in this definition.

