8.12 Expedited Reporting Of Serious Adverse Events

Any AE that is considered serious must be reported to the device manufacturer, EKOS Corporation, within 24 hours of the site's knowledge of the event throughout the study. The Investigator will enter into EDC as much of the information listed below is available within 24 hours. An automatically generated email notification will be sent to EKOS when the event is classified as a Serious Adverse Event in EDC.

- a. Subjects demographics
- b. Pre-existing conditions
- c. The adverse event's description
- d. Date and time of AE onset
- e. Severity
- f. Treatment
- g. Results of diagnostic testing
- h. Duration of sequelae
- i. Outcome (if known)
- j. Information on suspected medications

When a device-related SAE is reported, the device must be retained and returned to EKOS (see above for address for return devices). The EKOS representative may contact the Investigator to collect additional information on EKOS.

When reporting a death, the primary event or condition that caused or contributed to the fatal outcome will be reported as the serious adverse event. Death would be reported as the outcome of the serious adverse event. If the cause of death is unknown at the time of reporting, record “unknown cause of death.”

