8.13 Safety Monitor

A safety monitor will review all AEs, adjudicate all SAEs and major bleeding events during the study, as well as assess freedom from major harm occurring between enrolment and 30 days for each subject. The safety monitor will determine if the AE meets the definition of serious and unexpected and will notify EKOS if the number or type of events is of concern.

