11.2 Anticipated Risks Of APT Procedure

Anticipated risks of the APT Procedure are categorized as likely, less likely, and rare.

Likely

1. Anxiety related to undergoing the APT Procedure
2. Discomfort or bruising at sites for blood draws, intravenous line placement, or EkoSonic® catheter placement
3. Discomfort from mandatory immobility during the APT Procedure.

Less likely

1. Infection, pre-syncope, or syncope due to intravenous line or catheter placement or additional peripheral blood draws needed to monitor therapy
2. Hematoma at the venous access site
3. Major bleeding requiring transfusion of blood products
4. Nausea and vomiting
5. Adverse reaction to iodinated contrast or other medications

6. Local discomfort during placement of the EkoSonic® Device
7. Limiting the dose of r-tPA and infusion time could potentially result in ineffective treatment of the study subject.

Rare

1. Adverse drug reaction to r-tPA
2. Severe allergic reaction (such as anaphylaxis) to iodinated contrast or other medications
3. Anesthesia complications
4. Post-procedure wound complications
5. Renal failure requiring hemodialysis
6. Vascular complications (such as dissection, perforation, vasospasm, pseudo aneurysm, occlusion, and arteriovenous fistula)
7. Thromboembolism
8. Recurrent PE
9. Fatal, life-threatening, or intracranial hemorrhage or stroke
10. Severe internal bleeding (such as gastrointestinal or retroperitoneal) that requires surgical or interventional laboratory intervention
11. Device-related trauma to cardiac structures (such as heart valves)
12. Death
13. Other rare or unforeseen adverse effects

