At select participating sites: In addition to the vital signs specified in Section 7.4, bedside vital signs including, systolic/diastolic blood pressure, heart rate, respiratory rate, capillary refill time and SpO2 will be recorded at the start of the APT Procedure, and at each 30 minute interval until 4 hours post-completion of the APT Procedure. Along with the echocardiograms specified in Section 7.7, limited echocardiograms performed at the bedside for RV/LV ratio measurements will be obtained hourly after the start of the APT Procedure through 4 hours post procedure.

Scatterplots of RV/LV ratio (y-axis) vs vital sign measures (x-axis) and of change in RV/LV ratio vs changes in vital sign measures will be presented to assess the correlation of change in clinical parameters (vital signs) with change in markers of RV strain (RV/LV ratio), and associated Pearson or Spearman correlation coefficients, where applicable.

Subject Set = Safety Subject Set for (19 – 23)

- 21) Major Bleeding Events within 72 hours of initiation of APT*
- 22) Technical Procedural Complications (*captured on the EkoSonic Device CRF as “Was this device successfully placed and used for treatment?”; make this a by-patient listing*)
- 23) Symptomatic Recurrent PE and Symptomatic Recurrent PE up to Day 365 (Confirmed by imaging)
- 24) All cause mortality up to Day 30 and all cause mortality up to Day 365 (*note: per AE and study exit CRFs*)
- 25) Adverse Events (*Run tables for AEs up to Day 30: AE start date ≤ Date of 30 Day Follow Up Visit per Follow-Up CRF*)
 - a) All reported events
 - b) Related to interventional procedure (not EKOS system)
 - c) Related to EKOS system
 - d) Related to thrombolytic drug
 - e) Related to anticoagulant drug
 - f) Bleeding events (*all site reported bleeding events, make tables for:*
-All reported bleeding events
-Those within 72 hours of APT start
-Those related to:
-interventional procedure (not EKOS system)
-EKOS system
-thrombolytic drug
-anticoagulant drug
 - g) SAEs

Also run analyses for (g) through Day 365, including those through 30 days.

26) Freedom from major harm occurring between enrolment and 30 days and assessed by the Safety Monitor using the following criteria:

- a. Mortality – all cause and PE related
- b. CV collapse: Defined as one or more of the following:
 - i. >40mmHg drop in SBP (for >15 minutes from documented blood pressure as an in-patient) despite IV fluid challenge and absence of new atrial arrhythmia.

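### Protocol 8.2 defines a life-threatening event by what a worse form of it might have done, so read literally it admits minor bleeds and can make SAE counts inflated and inconsistent

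*Protocol*

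**What the plan says.** Protocol 8.2 lists six outcomes that make an adverse event serious. The second is "Life-threatening (had the event occurred in a more severe form, might have caused death". The lead-in says that an event qualifies if, "in the view of either the investigator or sponsor, it results in any of the following outcomes", so one of the two views is enough. The sixth outcome covers important medical events that meet none of the earlier criteria, where medical judgment finds that "they may jeopardize the subject and may require medical or surgical intervention to prevent one of the outcomes listed in this definition".

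The classification is used in several places:

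- Protocol 8.12: "Any AE that is considered serious must be reported to the device manufacturer, EKOS Corporation, within 24 hours of the site's knowledge".
- Protocol 8.13: the safety monitor reviews all AEs and adjudicates all SAEs and major bleeds. "The safety monitor will determine if the AE meets the definition of serious and unexpected".
- Protocol 6.9 and 7.11: non-anticoagulant medication is recorded only if it was prescribed to treat an SAE.
- Protocol 8.9, item 7: serious bleeding events are recorded to Day 365.
- SAP 2.4 and Appendix 1, item 25: AE tables stop at Day 30, except for SAEs. For those the instruction is: "Also run analyses for (g) through Day 365, including those through 30 days".

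The SAP contains no SAE definition of its own.

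**The concern.** The bracketed words replace the usual question, whether this event put the subject at risk of death, with another: could a worse version have done so? For bleeding under thrombolysis and anticoagulation, the answer to the second question is nearly always yes. A site that applies the words and a site that applies the ordinary meaning of life-threatening would classify the same small bleed differently.

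At stake are the SAE count, its comparability between sites and arms, and the workload of expedited reporting. SAEs are also the only general AE category that the SAP tabulates beyond Day 30, so for those later tables the definition decides what the reader sees.

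**Working it through.** The point turns on wording, and the plan states no SAE rate to reproduce. The check sets the passages side by side.

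**1. Does the literal rule have a lower limit?** Protocol 11.2 gives both ends of the bleeding range. It lists bruising at access and blood-draw sites as likely, "Hematoma at the venous access site" as less likely, and "Fatal, life-threatening, or intracranial hemorrhage or stroke" as rare. On the protocol's own list, then, minor bleeding has a more severe form that can kill. Taken literally, criterion 2 is met.

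**2. Does it fit the rest of the list?** Criterion 6 asks whether the actual event may jeopardize the subject. Criterion 2, taken literally, asks only about a hypothetical event, which is a weaker condition. The fallback criterion is then stricter than the one it is meant to supplement and has little left to catch. Protocol 8.11 grades severity as it was experienced. Criterion 2 lets an event graded mild be serious because of a severity it never reached.

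**3. Is it corrected elsewhere?** No. The safety monitor decides whether an AE meets the definition of serious, and the only definition is in 8.2.

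**4. Which classification reaches the table?** SAP Appendix 1, item 25(f), specifies site-reported bleeding events. Item 25(g) does not say whether seriousness is as reported by the site or as adjudicated. Differences between sites could therefore reach the SAE table unfiltered.

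**5. What is outside its reach?**

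- The primary safety endpoint uses the ISTH criteria (Protocol 3.4.1 and 8.8; SAP 1.4.1).
- Freedom from major harm has its own component list (Protocol 3.3, item 3).
- Recurrent PE and mortality to Day 365 are tabulated separately (SAP Appendix 1, items 23 and 24).

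**6. Can the size be estimated?** Let s be the share of subjects with a truly serious event and m the share of the rest who have only a minor bleed. Suppose that every such bleed is classed as serious. The reported SAE share is then s + (1 − s) × m. Neither s nor m is in the documents; the values below are assumptions.

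| s | m = 0.05 | m = 0.30 | ratio to s |
|---|---|---|---|
| 0.05 | 0.05 + 0.95 × 0.05 = 0.098 | 0.05 + 0.95 × 0.30 = 0.335 | 1.95 to 6.7 |
| 0.10 | 0.10 + 0.90 × 0.05 = 0.145 | 0.10 + 0.90 × 0.30 = 0.370 | 1.45 to 3.7 |
| 0.20 | 0.20 + 0.80 × 0.05 = 0.240 | 0.20 + 0.80 × 0.30 = 0.440 | 1.2 to 2.2 |

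The ratio runs from 1.2 to 6.7 depending only on what is assumed, and universal literal use is itself an assumption. This shows the direction of the error and gives no estimate of its size. With 29 UK subjects (SAP synopsis) and an assumed equal split, an arm has about 10 subjects, so one subject is about 10 percentage points. That holds for any event in an arm of this size and is not evidence about this definition.

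**The case against.** The strongest reply is that nobody would read the bracket that way. The headword is still life-threatening, and classification is a matter of judgment. Elsewhere the protocol uses the term in its plain sense: section 8.8 places it beside death and chronic sequelae, and section 11.2 lists life-threatening haemorrhage apart from haematoma. No document shows a site applying the literal reading. This is fair, and it is why the conclusion is that counts *can* be inflated, not that they are. It does not remove the defect, because the bracket is the only stated explanation of the criterion and one literal reader is enough.

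A reader might go further and infer that the SAE tables lose their meaning, or that true serious events are hidden among minor ones. The documents do not support either inference:

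- Events are tabulated by worst severity (Protocol 10.4; SAP 2.4), so a mild event classed as serious would show as mild.
- The safety monitor reviews all AEs, so seriousness does not decide what the monitor sees. A single central reader also reduces variation between sites, although with the same definition.
- The literal error runs toward over-reporting, so it would not cause a serious event to be missed.
- The SAE tables are descriptive. No SAE hypothesis test or numeric SAE threshold is planned.

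Nor can one infer that bleeding after Day 30 is lost unless it is serious. Protocol 8.7 continues to collect AEs related to bleeding, VTE and EKOS treatment, although 6.7 and 8.6 are narrower. What remains is that the SAP's AE tables extend only SAEs past Day 30.

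**Conclusion.** The concern holds as a drafting defect with limited reach. Criterion 2 of Protocol 8.2 tests a hypothetical worse event. Followed literally, it admits minor bleeds, undercuts criterion 6 and allows the same event to be classified differently by different sites. It bears on 24-hour reporting, SAE adjudication, concomitant-medication recording and the descriptive SAE tables through Day 30 and Day 365. It does not bear on ISTH major bleeding within 72 hours or on the major-harm components. The effect on the SAE count is upward, and its size cannot be estimated because the documents give neither an SAE rate nor a minor-bleed rate. The conclusion assumes only that at least some readers apply the bracket as written.

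**What to change.** 1. Reword criterion 2 of Protocol 8.2, for example: *Life-threatening: the subject was at risk of death from the event as it occurred; this does not include an event that might have caused death had it been more severe.*
2. Have the safety monitor re-adjudicate, under that wording, any SAE that rests on criterion 2 alone.
3. State in SAP Appendix 1, item 25(g), that the SAE tables use this adjudicated seriousness.

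**Cost.** The protocol change is one line and needs no new data, but it is not free. UK enrolment ended in March 2019 and the SAP is dated 8 November 2019, so every UK subject had passed Day 30 and most classifications had probably been made. Re-adjudication is therefore part of the cost, though small with 29 subjects. Some were still within their one-year follow-up at that date, so later events could be classified under the new wording from the start. Fewer events will be classed as serious; those up to Day 30 stay in the all-AE tables. Item 25 is not marked for pooling in Appendix 1. If SAE counts are nevertheless pooled or shown beside those of the first 100 treated subjects, a note should say which definition was applied to them.

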8.3 Unexpected Adverse Events

An AE is considered “unexpected” if it is not listed in the IFU or package insert or is not listed at the specificity or severity that has been observed.

8.4 Pre-Existing Medical Conditions

A pre-existing medical condition is one that is present at the start of the study. Pre-existing medical conditions should be reassessed during the trial and reported as an AE only if the frequency, severity, or character of the conditions worsens significantly or unexpectedly during the study. When reporting such adverse events, the description should convey that the pre-existing condition has changed by including applicable descriptors (for example, “more frequent” headaches). Scheduled hospitalizations required for diagnostic or elective surgical procedures for the management of unchanged pre-existing medical condition should not be considered AEs.

8.5 Device Deficiency, Device Failures and Malfunctions

Manufacturers must report device-related deaths, serious injuries and malfunctions to the country-specific regulatory agency whenever they become aware of information that reasonably suggests that the reportable event occurred (one of their devices has or may have caused or contributed to the event).

8.5.1 Definitions

A device failure is defined as the device is used in accordance with the IFU, but does not perform according to IFU and negatively impacts the treatment.

A device malfunction is defined as an unexpected change to the device that is contradictory to the IFU and may or may not affect device performance.

8.5.2 Reporting Requirements

All device failures and malfunctions will be documented on the eCRF within one working day after the designated study site personnel first learn of the event, and reported to the IEC/IRB (if required) within the IEC/IRB required timeframe. The Investigator will enter data into EDC within one working day and an automatically generated email notification will be sent to EKOS.

Device Malfunction

In the event of a device malfunction contact the BTG EKOS representative or EKOS Helpline for assistance. If the device cannot be restarted or is damaged in some way, if possible, the malfunctioning device will be replaced to continue ultrasound treatment for the desired length of time. If it is not possible to replace the device, thrombolytic infusion can be continued without the activation of ultrasound. The duration of the ultrasound will be recorded. The malfunctioning device will be retained for return to EKOS. When the malfunction is reported to EKOS, product return information will be provided.

Contact Information

For United States: [REDACTED]

For United Kingdom: [REDACTED]

8.6 Documentation Of Adverse Events

AEs will be reported when noted during the hospitalization for the initial treatment and in the subject's medical record through the 30 day follow-up period. Subjects will be encouraged to report AEs spontaneously or at follow-up visits in response to non-directed questioning by Investigator or Research Coordinator (for example, in response to the question "How has your health been since your last visit?"). If it is determined that an AE has occurred, the study staff member entering data into the eCRF will obtain all of the information necessary to complete the AE section. Serious adverse events including VTE events will be reported through the 365 day study. Subjects will be specifically asked about visits to a physician, hospitalizations and other events that meet the definition of serious.

8.7 Reporting And Duration Of AE Reporting Period

Because the EKOS is a commercial medical device, Investigators will comply with any hospital user reporting requirements. All observed or reported AEs including type of event, severity and relationship to the procedure, device use, thrombolytic and anticoagulant drug use will be recorded in the eCRF during hospitalization and through 30 day follow-up. At subsequent visits, SAEs and AEs related to venous thromboembolism, bleeding events or the EKOS treatment will be collected. Previously reported AEs will continue to be followed to resolution.

